### ***30-minutes Post-Vaccination Observation Period***

Unsolicited systemic AEs occurring within 30 minutes after each vaccination will be presented in summary safety tables, analyzed according to their causality (relationship to the investigational product) and Grade 3 intensity.

### ***Solicited Reactions***

The solicited injection site reactions and the solicited systemic reactions will be presented according to the term listed in the eCRF, separately.

The solicited injection site and systemic reactions will be analyzed within 7 days after each vaccination.

Each type of solicited reactions will be presented after each injection according to:

*- Maximum intensity during the solicited period:*

- Grade 1
- Grade 2
- Grade 3

*- Time of onset categories are in [Table 5.3](#)*

**Table 5.3: Time of onset categories for solicited reactions**

	Injection Site Reactions	Systemic Reactions
Post each dose in the primary series, booster dose	D0-D3 D4-D7	D0-D3 D4-D7

*- Range of number of days of occurrence categories are in [Table 5.4](#)*

**Table 5.4: Range of number of days of occurrence categories for solicited reactions during the solicited period**

	Injection Site Reactions	Systemic Reactions
Post each dose in the primary series, booster dose	1 - 3 days 4 - 7 days 8 days	1 - 3 days 4 - 7 days 8 days

Note: Cohort 1 planned to receive 3 doses and Cohort 2 planned to receive 2 doses, respectively, in the primary series.

- *Range of overall number of days of occurrence categories are in Table 5.5*

**Table 5.5: Range of overall number of days of occurrence categories for solicited reactions**

	Injection Site Reactions	Systemic Reactions
Post each dose in the primary series, booster dose	1 - 3 days* 4 - 7 days 8 days or more Missing end date	1 - 3 days* 4 - 7 days 8 days or more Missing end date

\* For solicited reactions still ongoing at D08 after each dose, the range of overall number of days of occurrence category will be 2-3 days, 4-7 day, 8 days or more, and missing end date.

Note: Cohort 1 planned to receive 3 doses and Cohort 2 planned to receive 2 doses, respectively, in the primary series.

- *Action Taken:*

- Missing
- None
- Medication
- Health care provider contact
- Hospitalization
- Discontinuation of study vaccination

Solicited reaction after any injection in the primary series

“After any injection” is for primary series only, means after all scheduled vaccine injections of the primary vaccination series, and at least after the first vaccine injection (D0).

The solicited reaction will be presented after any injections in the primary series and presented after booster vaccination according to:

- *Occurrence during the solicited period for solicited reactions, and overall occurrence for solicited reactions still ongoing at D08*
- *Time of onset period*
- *Intensity grade: the maximum intensity grade will be computed during the solicited period for all solicited reactions*

### ***Unsolicited Adverse Events***

The unsolicited systemic AEs will be analyzed per cohort:

- Cohort 1
  - “Between the first and the second vaccination”, which corresponds to AEs reported at V02 and occurring after the first dose \*
  - “Between the second and the third vaccination”, which corresponds to AEs reported at V03 and occurring after the second dose †
  - “Up to 28 days after the third vaccination”, which corresponds to AEs reported at V05 and occurring after the third vaccination
  - “Up to 28 days after any vaccine injection in the primary series”, which corresponds to AEs belonging to any of the above three categories
  - “Up to 28 days after booster dose”, which corresponds to AEs reported at V07 or V08 and occurring after booster dose, for an adult subset
- Cohort 2
  - “Between the first and the second vaccination”, which corresponds to AEs reported at V02 and occurring after the first dose \*
  - “Up to 28 days after the second vaccination”, which corresponds to AEs reported at V03 or V04 and occurring after the second vaccination
  - “Up to 28 days after any vaccine injection in the primary series”, which corresponds to AEs belonging to any of the above two categories
  - “Up to 28 days after booster dose”, which corresponds to AEs reported at V09 or V10 and occurring after booster dose, for an adult subset

The unsolicited injection site reactions will be analyzed within 28 days (from D0 to D28) after each vaccination, and within 28 days after any vaccination. An unsolicited injection site reaction

\* For subjects interrupting their vaccination schedule after the first injection, unsolicited AEs until 28 days after the first dose will be collected

† For subjects interrupting their vaccination schedule after the second injection, unsolicited AEs until 28 days after the second dose will be collected

(excluding SAE and AESI) reported with an onset > 28 days after a vaccination will not be included in the safety analysis, but will be listed separately.

The unsolicited systemic AEs will be analyzed between each vaccination if vaccinations are separated less than 28 days, or up to 28 days after each vaccination, if the next vaccination is interrupted, and up to 28 days after any vaccination. An unsolicited systemic AE (excluding SAE and AESI) reported with an onset > 28 days after vaccination will not be included in the safety analysis, but will be listed separately.

Note: An unsolicited AE with missing time of onset will be considered to have **occurred within or up to 28 days after the last vaccination** (computed according to [Section 4.3.1.2.3](#)), so will be included in safety analysis.

The unsolicited AEs will be summarized in the safety overview and analyzed according to their nature (SOC and PT of the MedDRA classification), causality (relationship to the vaccine injection as assessed by the investigator), maximum intensity, time of onset and duration.

The occurrence of any unsolicited AE will be presented after any and each injection according to:

- *Maximum intensity:*

- Missing
- Grade 1
- Grade 2
- Grade 3

- *Time of onset categories*

- Missing
- D0-D3
- D4-D7
- D8-D14
- >=D15

- *Maximum duration:*

- Missing
- 1 - 3 days
- 4 - 7 days
- 8 - 14 days
- 15 days or more

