- 8) Only subjects from pediatric subjects and adult subjects in Primary Series Cohort 1 will receive the 3rd injection (VAC3) from the unblinded staff member in the opposite arm as compared to VAC2 and will stay at the center for the 30-minute observation period following vaccination. Safety assessment will be made by the blinded Investigator, different from the person performing the vaccination.
- 9) DC3 will be provided only to pediatric subjects and adult subjects in Primary Series Cohort 1 or the subjects' parent/ LAR.

10) The source documents and the relevant CRF pages for this visit will be completed.

11) Remind the subject or subjects' parent/ LAR to bring back the DC when they return for V04 at a specified date and time.

12) Remind the subject or subjects' parent/ LAR to notify the site in case of a SAE and AESI.

13) For woman of childbearing potential: remind the subject to notify the site in case of pregnancy.

14) Complete the relevant source document information and CRF pages for this visit.

V04 (42 [\pm 3] days after VAC1) for Pediatrics and Adults in Primary Series Cohort 1: Collection of Safety Information and Blood Sample

- 1) DC3 will be checked by the blinded Investigator/ staff, different from the person performing the vaccination and will be given back to subjects or subjects' parent/ LAR.
- 2) Conduct a physical examination, including temperature.
- 3) A blood sample will be collected only (3 mL for subject 1 year to < 2 years, 5 mL for subjects \geq 2 to < 18 years, and 6 mL for subjects \geq 18 years).

- 4) Collect ongoing medications including other therapies in the source document and reportable concomitant medication in the CRF (see [Section 6.9](#)).
- 5) Subject or subject's parent/ LAR will be reminded to notify the site in case of SAE and AESI.
- 6) The source documents and relevant CRF pages for this visit will be completed.

V05 (56 [\pm 3] days after VAC1) for Pediatrics and Adult Subjects in Primary Series Cohort 1: Collection of Safety Information

- 1) DC3 will be collected and checked by the blinded Investigator/staff, different from the person performing the vaccination.
- 2) Conduct a physical examination.
- 3) Give the MA1 to record any SAEs or AESIs that may occur during the safety follow-up.
- 4) Collect ongoing medications including other therapies in the source document and reportable concomitant medication in the CRF (see [Section 6.9](#)).

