- 9) Subject will be reminded to notify the site in case of SAE and AESI.
- 10) For woman of childbearing potential: remind the subject to notify the site in case of pregnancy
- 11) The source documents and the relevant CRF pages for this visit will be completed.
- 12) Remind the subject to bring back the DC3 when they return for V09 at a specified date and time.

V09 ([between 24 months and up to 36 months+14D] +14 [+1] days after VAC1): Collection of Safety Information and Blood Sample - for Adult Subjects in Immunogenicity Persistence and Booster Phase Cohort 2

- 1) DC3 will be checked by the Investigator/staff.
- 2) A blood sample will be collected (6 mL).
- 3) Collect ongoing medications including other therapies in the source document and reportable concomitant medication in the CRF (see [Section 6.9](#)).
- 4) Subject will be reminded to notify the site in case of SAE and AESI.
- 5) The source documents and relevant CRF pages for this visit will be completed.

V10 ([between 24 months and up to 36 months+14D] +28 [±3] days after VAC1): Collection of Safety Information and Blood Sample - for Adult Subjects in Immunogenicity Persistence and Booster Phase Cohort 2

- 1) DC3 will be collected and checked by the Investigator/staff.
- 2) Conduct a physical examination.
- 3) Give the subject the MA to record any SAEs or AESIs that may occur during the safety follow-up.
- 4) Collect ongoing medications including other therapies in the source document and reportable concomitant medication in the CRF (see [Section 6.9](#)).
- 5) Subject will be reminded to notify the site in case of SAE or AESI.
- 6) The source documents and relevant CRF pages for this visit will be completed.
- 7) Complete the study termination record.

6-month Safety Follow-up PC after the Booster Injection (M30 up to M42 +14D): for Adult Subjects in Immunogenicity Persistence and Booster Phase Cohort 2

Subject will be contacted by phone by the Investigator/staff 6 months after the booster vaccination. Information recorded in MA will be checked.

Further details on the visit procedures can be found in the Operating Guidelines.

5.1.4.3 Follow-up for Cohorts 1 and 2

Follow-up of Subjects With RVNA Titer ≤ 0.5 IU/mL After Completion of the 2- or 3-dose PrEP Regimen With Rabies Vaccine (and Booster Dose for Adult Subset):

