### 5.2.2.1 Per-Protocol Analysis Set for D42

The PPAS for D42 is a subset of the FAS which will be used for primary objective assessment at D42 (V04) for subjects in Cohort 1. The subjects presenting with at least one of the following relevant protocol deviations before D42 (ie, 14 days after the third vaccine injection) will be excluded from the PPAS for D42:

- Subject did not meet all protocol-specified inclusion criteria or met at least one of the protocol-specified exclusion criteria
- Subject did not complete the 3-dose vaccination schedule
- Subject received a vaccine other than the one that he / she was randomized to receive
- Preparation and / or administration of vaccine was not done as per-protocol

- Subject did not receive vaccine in the proper time window
  - Vaccination dose 2 in [D07-D09]
  - Vaccination dose 3 in [D25-D31]
- Subject did not provide post-dose 3 serology sample at V04 in the proper time window [D11, D17] post the third vaccination (ie, Vac3 +14D ±3D), or a post-dose 3 serology sample was not drawn at V04
- Subject received a protocol-prohibited therapy/medication/vaccine (belonging to categories 2 and 3) before V04 (D42)
- Subject's serology sample is missing or did not produce valid test results at D0 or D42
- Seropositive subject at D0, ie, RVNA titer  $\geq$  LLOQ
- Subject developed a protocol-specified withdrawal criterion during the study but was not withdrawn before V04 (D42)

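### The SAP's Cohort 1 post-dose-3 category for unsolicited systemic AEs names V05 but not V04, which conflicts with its own onset-based rules and its parallel categories

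*SAP*

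**What the plan says.** SAP 5.1.2.2, *Unsolicited Adverse Events*, lists the analysis periods for unsolicited systemic events by cohort and ties each to the visits at which the events are reported.

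- Cohort 1, after dose 3: "which corresponds to AEs reported at V05 and occurring after the third vaccination".
- Cohort 1, any primary injection: "which corresponds to AEs belonging to any of the above three categories". Those three rest on V02, V03 and V05.
- Cohort 1, after the booster: "which corresponds to AEs reported at V07 or V08 and occurring after booster dose, for an adult subset".
- Cohort 2, after dose 2: "which corresponds to AEs reported at V03 or V04 and occurring after the second vaccination".
- Cohort 2, after the booster: "which corresponds to AEs reported at V09 or V10 and occurring after booster dose, for an adult subset".

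In Cohort 1, V04 is a safety visit. Protocol 5.1.4.1 heads it "V04 (42 [\pm 3] days after VAC1) for Pediatrics and Adults in Primary Series Cohort 1: Collection of Safety Information and Blood Sample". The assessment of injection site reactions and systemic events is ticked at V04 in SAP Table 3.2. Protocol 9.2.1.3 has the investigator ask at every visit about events since the previous one.

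**The concern.** No Cohort 1 primary-series category includes V04, although V04 sits inside the 28 days after dose 3. A programmer who follows the visit list would leave out unsolicited systemic events reported at V04, both from the dose 3 rate and from the any-dose rate.

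Describing safety after each injection in each age group is a secondary objective (Protocol 2.2; SAP 2.2). For unsolicited events the SAP takes as denominator all subjects vaccinated at the dose, or with at least one dose. Events missing from the numerator therefore lower the rate directly. A subject seen at V04 but not at V05 would stay in the denominator with no dose 3 systemic event possible.

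**Working it through.** The plan states no figure on this point, so there is none to reproduce. The check compares passages and adds day arithmetic.

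**1. Timing (SAP Table 3.2).** Dose 3 is at D28, V04 at D42 and V05 at D56.
- V04 after dose 3: 42 − 28 = 14 days. The per-protocol set for D42 (SAP 5.2.2.1) accepts the V04 sample from day 11 to day 17.
- V05 after dose 3: 56 − 28 = 28 days.

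**2. Parallel categories.**

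| Period | Visits in the window | Visits named in the SAP |
|---|---|---|
| Cohort 1, dose 3 | V04, V05 | V05 |
| Cohort 1, booster | V07, V08 | V07 or V08 |
| Cohort 2, dose 2 | V03, V04 | V03 or V04 |
| Cohort 2, booster | V09, V10 | V09 or V10 |

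In all four periods the diary is checked at the first visit and collected at the second (Protocol 5.1.4). Only the first row leaves out the earlier visit.

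**3. Other SAP rules on the same events.**
- 4.3.1 analyses unsolicited events up to 28 days after any and each vaccination.
- 4.3.1.2.3 assigns an event to a dose by its start date when that date is complete and is not a vaccination date.
- The safety endpoint list in 5.1.2.2 takes systemic events between doses and for 28 days after the last.
- The closing text on unsolicited systemic events excludes only onset later than 28 days.
- The tables after each injection show onset at D0-D3, D4-D7, D8-D14 and D15 or later. The first three rows are largely the interval that precedes V04.

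These rules would include the events that the visit list leaves out.

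**4. Events with no onset date.** SAP 5.3.2.5 includes these according to the visit collected. One collected at V04 in Cohort 1 has no clearly named category. The note on missing onset in *Unsolicited Adverse Events* points to inclusion after the last dose, but the visit list does not say where.

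**5. Span exposed under the literal reading.**
- Dose 3: 14/28 = 50% of the window; 11/28 = 39% to 17/28 = 61% over the V04 range.
- Any dose (D0 to D56): 14/56 = 25%.
- Subjects: 505 children + 505 adults = 1010 at most.

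**6. Illustration only.** Assume a constant hazard and that every event with onset before V04 is reported at V04. With true 28-day incidence p and V04 on day d after dose 3, the tabulated incidence is 1 − (1 − p)^((28 − d)/28).

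| True p | d = 11 | d = 14 | d = 17 |
|---|---|---|---|
| 5% | 3.1% | 2.5% | 2.0% |
| 10% | 6.2% | 5.1% | 4.1% |
| 20% | 12.7% | 10.6% | 8.4% |
| 30% | 19.5% | 16.3% | 13.1% |

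A true any-dose incidence of 20% over 56 days would be tabulated as 1 − 0.8^(42/56) = 15.4%.

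**The case against.** The strongest reply is that nothing need be lost. The SAP line does not say that V05 is the sole visit, the category's label promises the full 28 days, and the rules in step 3 select by onset. Diary card 3 is also handed back at V04 and collected at V05, so its whole content could fairly be called reported at V05.

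Most of this stands. The omission is probably a drafting slip, and a programmer working from onset dates would never meet it. The diary argument is weaker: it applies equally to the other three periods, where the earlier visit is nevertheless named. Nor do the onset rules clearly settle where an event without an onset date belongs.

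A reader might infer that Cohort 1 would look better tolerated than Cohort 2. The documents do not support that. The safety objective compares vaccines within age group, and no safety comparison between cohorts is planned. Even on the literal reading the Cohort 1 any-dose category spans about 56 − 14 = 42 days against 35 in Cohort 2, so no direction is established.

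A reader might also take 50% as the share of events lost. It is a share of time; the number of events depends on when they occur and how many are entered at V04.

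**Conclusion.** The definition is wrong as written and inconsistent with the rest of the SAP. The consequence is conditional: if the tables follow the visit list, unsolicited systemic events reported at V04 are left out and the Cohort 1 dose 3 and any-dose rates are understated. If they follow onset dates, nothing is lost. The documents do not say which will be done, and the size is unknown because they give no event rates. The percentages in step 6 rest on its two assumptions and are not estimates for this trial.

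Groups 1, 2 and 3 fall under the same rule, so the effect is mainly on absolute rates; the documents give no ground for a bias towards one vaccine. Solicited reactions, unsolicited injection site reactions, and the dedicated SAE and AESI tables use onset or date windows and are unaffected. The point deserves correction because the description of each dose is a stated objective and the edit is trivial.

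**What to change.** In SAP 5.1.2.2, *Unsolicited Adverse Events*, name V04 or V05 as the reporting visits for the Cohort 1 category after dose 3. The any-injection category is then complete without further change. Alternatively, define every category by onset date, from day 0 to day 28 after the dose or until the next dose, whatever the reporting visit, and state where events with a missing onset date are placed.

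Either option costs one short SAP edit. It needs no new data and leaves the hypothesis tests and power unchanged.

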### ***SAEs and AESIs***

The SAEs and AESIs, which are included in the unsolicited AEs, occurred during the study will be analyzed on the following periods for each cohort:

- Primary series
  - During the active phase of the primary series: from date of first vaccination (V01) to 28 days after the date of last exposure to study vaccine in the primary series (date of last exposure in the primary series + 28 days)
  - During the 6-month follow-up period of the primary series: from 29 days after the last exposure to study vaccine in the primary series (date of last exposure in the primary series + 29 days) to end of 6-month follow-up in the primary series (last visit date or contact date collected in eCRF in the primary series)
  - During the primary series: from date of first vaccination (V01) to end of 6-month follow-up in the primary series (last visit date or contact date collected in eCRF in the primary series)
- Between the end of 6-month follow-up of the primary series and before booster dose (V06 for Groups 1 to 3 [Cohort 1] or V08 for Groups 4 to 6 [Cohort 2]) of the adult subset (Note: for Cohort 2, only fatal or related SAEs are collected and AESI will not be collected during this period)
- Booster phase of the adult subset
  - During the active phase of the booster phase: from date of booster dose (V06 for Groups 1 to 3 [Cohort 1] or V08 for Groups 4 to 6 [Cohort 2]) to 28 days after the booster dose (V08 for Groups 1 to 3 [Cohort 1] or V10 for Groups 4 to 6 [Cohort 2])
  - During the 6-month follow-up period of the booster phase: from 29 days after the booster dose (V08 for Groups 1 to 3 [Cohort 1] or V10 for Groups 4 to 6 [Cohort 2]) to end of 6-month follow-up post booster dose (last visit date or contact date for booster phase collected in eCRF)
  - During the booster phase: from date of booster dose (V06 for Groups 1 to 3 [Cohort 1] or V08 for Groups 4 to 6 [Cohort 2]) to end of 6-month follow-up post the booster dose
  - During the whole study period: from date of first vaccination (V01) to end of 6-month follow-up in the booster phase (last visit date or contact date for booster phase collected in eCRF)

SAEs will be analyzed according to their nature (SOC and PT of the MedDRA classification), causality (relationship to the study vaccine), seriousness criterion and outcome.

AESIs will be analyzed according to their nature (SOC and PT of the MedDRA classification) and causality.

### 5.1.3 Exploratory Analyses

#### 5.1.3.1 Subgroups Analysis: Impact of Demographic Factors and Center

With the aim to provide the same standards and granularity in terms of investigational results across VRVg studies, and comply with health authorities requirements (3), the possible influence of following factors on the immunogenicity and safety results will be analyzed using descriptive statistics. Thus, the main immunogenicity and safety parameters will be described according to gender, age group, ethnicity (only if more than 5% of subjects had different ethnicity), race (only if more than 5% of subjects had different race), and center.

Race and ethnicity will be defined according to current guidelines (3).

Age groups are the following ones:

- Pediatric (<18 years): including 12 to 23 months, 2 to 11 years, and 12 to 17 years;
- Adult ( $\geq 18$  years): including 18 to 40 years, 41 to 64 years, and  $\geq 65$  years.

These exploratory analyses will be primarily performed on the FASI, FASI for Immunogenicity Persistence and FASI for Booster (for immunogenicity), or the SafAS and SafASB (for safety).

In case of any safety signal detected in the VRVg-2 vaccines, a statistical comparison will be performed between VRVg-2 group and each of the control groups (Verorab® and Imovax® Rabies) with a Fisher exact test in order to check for statistical significance (alpha=0.05, two-sided).

#### 5.1.3.2 Impact of the COVID-19 pandemic

To evaluate the possible impact of the COVID-19 pandemic on the study conduction, main immunogenicity and safety results, the following sensitive analyses will be performed but not limited to:

- Impact of COVID-19 pandemic on subject's disposition, based on enrolled subjects

Note: Subjects impacted by COVID-19 refers to subjects with at least one major/critical protocol deviation due to COVID-19, or who did not complete the study due to COVID-19, or who reported "VISIT NOT DONE" on safety follow up in pandemic form.

- Major or critical deviations due to COVID-19 by randomized group, based on randomized subjects.
- Immunogenicity analysis primarily based on FASI, FASI for Immunogenicity Persistency and FASI for Booster
  - Impact of COVID-19 pandemic on immunogenicity analysis.
  - Impact of medical history of suspected/confirmed COVID-19 pandemic on immunogenicity analysis.
  - Impact of the use of concomitant medications that are used during the study/or were used within 2 months before enrollment for treating/preventing COVID-19 (ie, Hydroxychloroquine and chloroquine) on immunogenicity.

- If any subjects received at least one dose of vaccination but took any concomitant medications for treating/preventing COVID-19 (ie, Hydroxychloroquine and chloroquine) within 2 months before enrollment, then the following immunogenicity analysis will be conducted based on PPAS
  - Immunogenicity of subjects who did not take any concomitant medications for treating/preventing COVID-19 (ie, Hydroxychloroquine and chloroquine) within 2 months before enrollment.
- Safety analysis based on SafAS and SafASB
  - Impact of COVID-19 pandemic on safety overview up to 28 days after any vaccination.
  - Impact of medical history of suspected/confirmed COVID-19 pandemic on safety overview up to 28 days after any vaccination.
  - Impact of the use of concomitant medications that are used during the study/or were used within 2 months before enrollment for treating/preventing COVID-19 (ie, Hydroxychloroquine and chloroquine) on safety overview up to 28 days after any vaccination.

Note: if only few subjects were impacted by COVID-19 (<5% in randomized subjects in the primary series or in the booster phase), only the corresponding listings will be provided instead of tables. Exception is the immunogenicity evaluation for the subjects who did not take any concomitant medications for treating/preventing COVID-19 (ie, Hydroxychloroquine and chloroquine) within 2 months before enrollment base on PPAS.

